9.2 Treatment Administration

Tipifarnib will be administered with food at a starting dose of 600 mg, po, bid daily on days 1-7 and 15-21 of 28-day treatment cycles.

The first study dosing (Cycle 1 Day 1) will take place in the study clinic. Tipifarnib will be administered orally with a meal in the morning and again approximately 12 hours later at approximately the same times each treatment day. Tablets should be swallowed whole with water (~8 oz. or 250 mL) but may be chewed or crushed if the Investigator deems it necessary. Use of percutaneous endoscopic gastrostomy tubes is allowed at the judgment of the Investigator. If a dose is vomited or partially vomited, it should not be replaced with a new dose.

Subjects may use proton pump inhibitors or H2 antagonists during the treatment portion of this study. However, subjects should be instructed to use antacids (magnesium or aluminum containing products) at least 2 hours before or after intake of oral study drug.

On Cycle 1 Day 1, the site will provide tipifarnib to the subject from bulk supplies. Subjects will be provided with diaries with instructions to record the date and time of each dose and asked to bring the diaries and tablet bottles to each clinic visit for subject compliance and drug accountability review by the site staff.

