Grade 2 Recurrent or Grade 3 Renal	Manage with BSC, including hydration and correction of electrolyte abnormalities, if appropriate. If not manageable, interrupt tipifarnib treatment until recovery to grade 1 or better	Upon recovery to ≤ grade 1, restart tipifarnib at the next lower dose level (see Table 2). If grade 2 or 3 renal toxicity recurs, upon recovery to ≤ grade 1, re-start tipifarnib at the next lower dose level (see Table 2).
Grade 2 non-tolerable Neurological	Manage with BSC. If not tolerable, interrupt tipifarnib treatment until recovery to grade 2 tolerable or better	Upon recovery to grade 2 tolerable or better, re-start tipifarnib at the next lower dose level (see Table 2).
		If grade 2 intolerable neurological toxicity recurs, upon recovery to grade 2 tolerable or better, re-start tipifarnib at the next lower dose level (see Table 2).
Grade 3 Neurological	Discontinue tipifarnib permanently	

In exceptional circumstances, dosing delays or skipping of dosing for reasons other than the management of toxicity will be allowed at the judgement of the investigator as long as 50% of the total dose is maintained in a given cycle.

Upon restarting tipifarnib following a treatment interruption, the cycle and dosing day are to be defined by the following:

- If a dose delay/interruption occurs and resolves within a cycle, dosing picks up where it left off
 - o For example, if a subject's treatment is held on Day 3, subject recovers 14 days later (nominal Day 17 in the cycle) and resumes tipifarnib treatment, the subject is considered to be dosing on Day 3 of the same cycle.
- If the delay goes beyond the cycle (> nominal day 28 of that cycle), upon recovery, the subject should be started at Day 1 of the next cycle.
 - o For example, if a subject's treatment is held on Day 3, subject recovers 30 days later (nominal Day 33 in the cycle) and resumes tipifarnib treatment, the subject is considered to be dosing on Day 1 of the next cycle.

Radiographic imaging for tumor response must maintain the fixed time schedule and is invariant to the drug exposure of the subject. Radiographic imaging will be performed at least once approximately every 8 weeks for 6 months, thereafter once approximately every 12 weeks. All other procedures/visits can follow the cycle's drug administration.

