10.9 Adverse Event Reporting Period

The adverse event reporting period for safety surveillance begins when the subject is included into the trial (date of first signature of informed consent) and continues through the trial's post-treatment follow-up period, defined as 30 days from the final administration of the trial treatment or immediately before initiation of any other anticancer therapy, whichever comes first.

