7. GENERAL STATISTICAL CONSIDERATIONS

7.1. Data Handling Conventions

Analyses will be performed using SAS® [SAS Institute 2011] Version 9.3 or higher.

- Summary tables for continuous variables will contain the following statistics: N (number of subjects in the population); n (number of subjects with data); mean; standard deviation; median; minimum; and maximum. Selected statistics may also include a 2-sided 95% normal approximation confidence intervals (CIs) on the mean.
- Summary tables for categorical variables will include: N (number of subjects in the denominator, X); n (number of subjects in the numerator, xx); and percent and will be presented in the format XX (XX.X%), where the percentage is in parentheses. Selected statistics also may include 2-sided 95% CIs for the percent.
- Date variables are formatted as yyyy-MM-dd for presentation.
- The baseline value for a given parameter is the last non-missing value prior to the first dose. A value is considered post-baseline if it is obtained after the first study drug administration.
- Change from baseline is calculated as (post-baseline result baseline result). Percent change from baseline is calculated as (change from baseline/baseline results * 100). If either the baseline or post-baseline result is missing, the change from baseline and percent change from baseline is set to missing as well.
- If days should be converted to months, the divisor of 30.4375 will be used (i.e., Months = Days / 30.4375)
- Data from all study centers will be pooled for all analyses.

Protocol KO-TIP-001

- Study day is defined as calendar date date of first treatment + 1 if the calendar date is on or after the date of first treatment, and calendar date date of first treatment if the calendar date is before the date of first treatment
- Measurements from unscheduled visits will be included in listings, but not summary tables, including laboratory tests performed at the site.
- Listings will be provided of all data collected in the electronic case report forms (eCRF).
- Wherever possible, data will be decimal aligned.
- For continuous variables, the following conventions will be made for significant digits:
 - Mean (xx.xx)
 - Standard deviation (x.xxx)
 - Median (x.xx)
 - Minimum and maximum (xx.x)

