10.1. Adverse Events

Adverse events will be coded using the latest available version of the Medical Dictionary for Regulatory Activities (MedDRA) Version 19.0. Treatment-emergent adverse events are defined as adverse events that start on or after the first dose of study drug and within approximately 30 days of the last administration of study drug. Adverse events will be summarized by the number and percentage of subjects who experienced the event, according to system organ class and preferred term. A subject reporting multiple cases of the same adverse event will be counted once within each system organ class and similarly counted once within each preferred term.

Unless specified otherwise, the denominator for these calculations will be the number of subjects who received at least one administration of tipifarnib, irrespective of the total number of doses or treatment cycles administered. These conventions will be appropriately modified to calculate AE incidence rates separately for each cycle that study therapy is administered. AE incidence rates may also be calculated based on other measures of subject exposure (e.g., total number of treatment cycles administered).

AE durations will be calculated using all TEAEs. For AEs that are still ongoing at the end of study, we will use either death or the last contact date as the end of AE stop date for calculation the duration of AEs. Median, minimum and maximum of AE durations will be reported.

AEs will also be summarized by NCI-CTCAE version 4.03 severity grade and by relationship to study drug. Additional summaries may also be provided for SAEs, and events resulting in the permanent discontinuation of therapy. All AEs will be included in individual subject listings.

An overall view of TEAEs will be provided, which will include the total number of TEAEs, number of subjects with TEAEs, study drug-related TEAEs, Serious TEAEs, study drug-related Serious TEAEs, Grade 3 or higher study drug-related TEAEs, deaths within 30-days of administration of study-drug, and AEs leading to permanent discontinuation of study drug. Additionally, a corresponding overall view of exposure-adjusted AE incidence will be provided, which will present exposure-adjusted incidence rates (calculated as the mean number of events per treatment cycle) with corresponding 95% confidence intervals.

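### The exposure-adjusted adverse event rate counts events for about 30 days after the last dose but divides by treatment cycles alone

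*SAP*

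**What the plan says.** SAP section 10.1 gives this definition of a treatment-emergent event: "adverse events that start on or after the first dose of study drug and within approximately 30 days of the last administration of study drug". Protocol section 12.2.2 uses the same window. Protocol section 10.9 closes adverse event collection somewhat earlier for some subjects; the follow-up period is "defined as 30 days from the final administration of the trial treatment or immediately before initiation of any other anticancer therapy, whichever comes first".

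Section 10.1 then plans an overview of these events, including deaths within 30 days of study drug, and a matching exposure-adjusted overview giving "exposure-adjusted incidence rates (calculated as the mean number of events per treatment cycle) with corresponding 95% confidence intervals". The same section adds that "AE incidence rates may also be calculated based on other measures of subject exposure (e.g., total number of treatment cycles administered"), which is again a count of cycles.

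On cycle length, Protocol section 9.2 gives tipifarnib "bid daily on days 1-7 and 15-21 of 28-day treatment cycles". Protocol section 9.5 sets the restart rule: "If a dose delay/interruption occurs and resolves within a cycle, dosing picks up where it left off".

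On intervals, the only general rule for a mean is in SAP section 7.1: "Selected statistics may also include a 2-sided 95% normal approximation confidence intervals (CIs) on the mean". No interval method is tied to the exposure-adjusted rate. The SAP does not say whether the mean is taken over subjects, over cycles or as a pooled ratio, nor how a part-completed cycle counts.

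**The concern.** An exposure-adjusted rate is meant to make groups with unequal treatment durations comparable. That requires every day on which an event could be counted to appear in the denominator. Here the days after the last counted cycle can contribute events but no exposure. This tail is about the same length for everyone, so its relative weight is greatest in subjects who stop early.

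The contrast in duration is real in this trial. The safety population takes in anyone with one dose (SAP section 6), while Protocol section 9.4 mentions several subjects treated for over a year. SAP section 8 says all data are summarized by cohort, and the cohorts are different tumour types. A cohort that progresses quickly could look more toxic than one that stays on treatment, at the same underlying event rate. Safety is the trial's only secondary objective.

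The undefined interval is a separate gap. Events cluster within subjects, so its validity depends on a choice the SAP leaves open.

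**Working it through.** The documents state no exposure-adjusted rate or expected event count, so there is no planned figure to reproduce.

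**Inputs from the documents**
- Cycle length 28 days, last planned dose on Day 21 (Protocol 9.2).
- Event window to 30 days after the last dose (SAP 10.1).
- Days counted above but not below the line: 30 − (28 − 21) = 23.

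**Assumption.** The event rate after the counted cycle is f times the earlier rate. The documents do not give f, so it is varied from 0 to 1.

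**Overstatement factor** for a subject with k cycles = (28k + 23f) / 28k.

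| Cycles (k) | f = 1 | f = 0.5 | f = 0.25 | f = 0 |
|---|---|---|---|---|
| 1 | 1.82 | 1.41 | 1.21 | 1.00 |
| 2 | 1.41 | 1.21 | 1.10 | 1.00 |
| 3 | 1.27 | 1.14 | 1.07 | 1.00 |
| 6 | 1.14 | 1.07 | 1.03 | 1.00 |
| 12 | 1.07 | 1.03 | 1.02 | 1.00 |

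For k = 1 and f = 1 this is (28 + 23)/28 = 51/28 = 1.82.

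**Part-completed cycles.** If the last dose is on Day 7 of Cycle 1 and the cycle counts as one, the factor at f = 1 is (7 + 30)/28 = 1.32. If the same exposure counted as 7/28 of a cycle, it would be 37/7 = 5.29. The SAP does not say which rule applies.

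**Effect on a group.** As a pooled ratio at f = 1, the factor is 1 + 23/(28 × mean cycles), or 1.41 at a mean of 2 cycles and 1.10 at a mean of 8. Two groups with the same true rate would then differ by 1.41/1.10 = 1.28, so the shorter-treated group looks 28% worse. Averaging subject-level ratios instead, with geometric cycle counts, gives 1.57 and 1.24.

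**Cycle length.** In the example in Protocol 9.5, a subject held on Day 3 resumes on nominal Day 17 and is treated as being on Day 3. That cycle runs 28 + 14 = 42 days and still counts as one, a factor of 42/28 = 1.5 in elapsed time.

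**Interval.** Coverage of a nominal 95% interval was simulated with 6,000 runs per setting. The assumptions were 2 events per cycle, geometric cycle counts with mean 5, and gamma variation in event rate between subjects.

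| Method | N = 75, no variation | N = 75, CV 50% | N = 75, CV 100% | N = 20, CV 50% | N = 20, CV 100% |
|---|---|---|---|---|---|
| Pooled Poisson | 95.0% | 61% | 35% | 61% | 38% |
| Cycle as unit | 95.0% | 70% | 56% | 69% | 56% |
| Mean over subjects | 94.6% | 94.9% | 93.6% | 92.7% | 90.1% |
| Ratio, clustered by subject | 94.3% | 93.5% | 91.5% | 90.2% | 86.8% |

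The interval is well short of 95% only when the subject is ignored and subjects differ. Subject-based methods are near nominal at N = 75 and lose some coverage in a group of 20.

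**The case against.** A reader might infer that the planned interval is too narrow. The documents do not support this, because the SAP names no method or unit for this rate. The optional rule in SAP 7.1 sits among summaries whose counts are numbers of subjects, so a mean over subjects is at least as natural a reading, and its coverage is close to nominal. What stands is that the method is unspecified and that two plausible choices would fail.

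A reader might also take 82% as the expected bias. It is the constant-rate value for one full cycle ending on Day 21. New anticancer therapy closes the tail early for some subjects. Protocol 5.1.1 gives a terminal half-life of about 19 hours and enzyme inhibition reversing within 3 to 7 days, so an unchanged rate of drug-related events over 30 days is an upper-end assumption. Zero is unlikely too: all treatment-emergent events count, related or not, and Protocol 10.7 has signs and symptoms accompanying progression recorded as adverse events.

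Nor is this the only safety summary that takes exposure into account. SAP 10.1 provides incidence by cycle, and by-cycle tables for Grade 3 or higher laboratory toxicities, fatigue and gastrointestinal events. Days on hold are off drug, so a denominator of treatment given can reasonably leave them out.

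Finally, time at risk is not neutral. If events stop when the cycle ends, it understates the on-treatment rate: 28/51 = 0.55 at one cycle, or 45% too low. This is a fair point about the remedy, but it does not excuse a numerator and denominator that cover different periods.

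**Conclusion.** The mismatch holds on the text. Events are counted to about 30 days after the last dose, exposure is counted in cycles, and no section of either document reconciles the two. For full cycles ending on Day 21, the overstatement ranges from 0% to 82% at 1 cycle, 41% at 2, 14% at 6 and 7% at 12. The upper values assume a constant event rate and the full 30-day tail; a halved rate gives about half of each. Cycles that stretch under Protocol 9.5 and the missing partial-cycle rule add further uncertainty about what one unit of exposure means. The table therefore does not fairly compare groups with different treatment durations.

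On the interval, the finding is an omission: it would be too narrow only if events were pooled as Poisson or cycles were treated as independent while subjects differ.

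The consequence is limited to one descriptive safety overview. No test, stopping rule or response rate analysis depends on it. It is still worth correcting, because the table's purpose is exposure adjustment and the correction is cheap.

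**What to change.** Amend SAP section 10.1 so that numerator and denominator cover the same period, in one of two ways:

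- **Time at risk.** Report treatment-emergent events per patient-month, from first dose to the earliest of last dose plus 30 days, start of new anticancer therapy, death or data cutoff. Months can use the SAP's own divisor of 30.4375 days. This also removes the dependence on cycle length.
- **Events within cycles.** Keep the per-cycle rate, limit the numerator to events starting within counted cycles, and state how a part-completed cycle counts. Cycles lengthened by holds would still count as one, and the table should say so.

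Under either option, state the averaging unit and take the 95% interval with the subject as the unit, for example from a Poisson or negative binomial model with a log-exposure offset (log time under the first option) and subject-level robust variance. Note that coverage may fall somewhat short in a cohort of about 20.

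The cost is SAP wording and, for the first option, one derived time variable. No new data are needed. The interval may widen: in the simulation with N = 75 and CV 50%, the clustered interval was 0.649/0.287 = 2.3 times the width of the pooled Poisson one. Under the first option the rate averages on-treatment and post-dose time, which the table footnote should state.

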10.2. Clinical Laboratory Evaluations

As noted above, hematological adverse events Grade 3 or above based on NCI CTCAE version 4.03 criteria will be summarized by treatment cycle and across all cohorts. A similar summary will be provided for selected chemistry toxicities, including: glucose, blood urea nitrogen (or uric acid), creatinine, sodium, potassium, chloride, calcium, magnesium, phosphorus, total protein, albumin, total bilirubin, alkaline phosphatase, alt, ast, gamma-glutamyltransferase, lactate dehydrogenase, bicarbonate (or total CO₂).

The data for clinical chemistry and hematology laboratory evaluations will be presented in listings. In addition to the results, these listings will present the normal range, toxicity grade, and clinical assessment (Normal; Abnormal, but not clinically significant; Abnormal, clinically significant) associated with evaluations.

Per subject laboratory comments for hematology, clinical chemistry, coagulation, urinalysis, serum tumor burden biomarker, and serum or urine pregnancy will also be displayed in listings.

10.3. Transfusion

The incidence of blood transfusion (platelets, red blood cells) will be summarized by treatment cycle and across all cohorts.

10.4. Vital Signs

Vital sign results (weight, blood pressure, pulse rate, respiratory rate, and temperature) will be summarized descriptively for each scheduled protocol time point. Changes will be calculated relative to the assessments at baseline.

Data on vital signs will be presented in listings.

10.5. ECGs

A summary of ECG overall category and shifts from screening will be provided for tests performed at Cycle 1 Day 1, Cycle 1 Day 7, end of treatment.

Data for all ECG overall assessments will be displayed in a listing.

10.6. Other Safety Measures

ECOG performance status per subject during the trial will be displayed in a listing.

Protocol KO-TIP-001

11. CLINICAL PHARMACOLOGY ANALYSES

None.

12. OTHER ANALYSES

Not applicable.

13. REPORTING CONVENTIONS

The table, listing and figure reporting layout will be detailed in the companion document *KO-TIP-001 Table, Listing and Figure Shells*.

14. CHANGES IN THE STATISTICAL METHODS FROM THOSE STATED IN THE PROTOCOL

Overall survival was added as an additional analysis.

Included sensitivity analysis for PFS and DOR on a subset of subjects.

15. TABLES, FIGURES, LISTINGS

Tables, listings and, if applicable, figures will be generated according to the companion document which details the layout of the output. Minor style deviation from specification defined in the shell document in the final production is permissible.

